6.8.3 Management of hypotension

Both study drugs can have the potential side effect of symptomatic hypotension and/or postural symptoms. Prior to any dose change blood pressure will be checked and up-titration will only occur if there is no symptomatic hypotension and systolic blood pressure is ≥ 100 mmHg. If appropriate, at the investigators discretion adjustments can be made to doses of diuretic and/or concomitant antihypertensive agents to facilitate the patient's ability to tolerate target study dose.

6.8.4 Management of angioedema

Angioedema is a potential side effect of combined RAAS and NEP inhibition. Angioedema has been reported in patients treated with sacubitril/valsartan. If angioedema occurs, study drug should be immediately discontinued and appropriate therapy and monitoring should be provided until complete and sustained resolution of signs and symptoms has occurred. It must not be re-administered. Any patients who experience angioedema during the trial will be withdrawn from the study.

6.9 Withdrawal of treatment

Any patient enrolled in the trial will be free to withdraw from the study at any time without giving reason and without prejudicing any further treatment/care. Following their involvement in the trial any patient withdrawing will be converted to an ACE-inhibitor or ARB as per local practice guidelines at an equivalent dose to their final study drug dose level.

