After assessing eligibility during screening, consenting patients who meet the study inclusion and exclusion criteria will be randomised in a double blinded 1:1 fashion to sacubitril/valsartan (target dose 97mg/103mg BD) or valsartan (target dose 160mg BD) and matching placebo. All patients will require to be tolerant (determined by clinical condition, SBP, and renal function) of a minimum dose of ACE inhibitor/ARB (ramipril 2.5mg BD or equivalent –*Table 4-1*) prior to randomisation. If on a lower dose at time of first screening, patients may be rescreened after an observed period of up-titration to a dose of ramipril 2.5mg BD or equivalent in-line with current standard of care and local practice. In order to minimise the potential risk of angioedema due to overlapping ACE and NEP inhibition all patients prescribed an ACE inhibitor pre-randomisation will undergo a minimum 36-hour “washout” period following randomisation prior to first dose of study drug.

Table 4-1 Total daily doses of commonly used ACE inhibitors or ARBs corresponding to ramipril 2.5mg BD (dose level 2 of study drug)

ACE inhibitor	Dose	ARB	Dose
Captopril	100mg	Candesartan	16mg
Enalapril	10mg	Irbesartan	150mg
Lisinopril	10mg	Losartan	50mg
Perindopril	4mg	Valsartan	160mg
Trandolapril	2mg		

[figure not shown]
Three dose levels of study medication will be administered in a stepwise titration (*Table 4-2*). Study drug will be started at dose level 2 (sacubitril/valsartan 49mg/51mg BD or valsartan 80mg BD) and up-titrated after 4 weeks to dose level 3 (sacubitril/valsartan 97mg/103mg BD or valsartan 160mg BD) if tolerated as assessed by clinical review (SBP and symptomatic hypotension) and laboratory evaluation (renal function). Patients already on a higher dose equivalent of ACE-inhibitor/ARB at dose level 2 (*Table 4-1*), may start at dose level 3 at investigators discretion taking into consideration the patient's prior dose level of ACE-inhibitor/ARB and clinical condition (SBP and renal function).

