5.3 Women of child bearing potential

Women of childbearing potential must be currently adhering to, or be willing to use, highly effective birth control methods for study treatment duration and for seven days thereafter including:

- Combined hormonal contraception (oestrogen and progestogen containing medication) either orally, intravaginally, or transdermally
- Progesterone only hormonal contraception either orally, injected, or implanted
- Progesterone only hormonal contraception either orally, injected, or implanted

- Intrauterine device (IUD)
- Intrauterine hormone release system (IUS)
- Bilateral fallopian tube occlusion
- Vasectomised partner
- Complete sexual abstinence where this is their preferred and usual lifestyle

Women of child bearing potential (WOCBP) comprises women who have experienced menarche and who have not undergone successful surgical sterilisation (hysterectomy, bilateral tubal ligation, or bilateral oophorectomy) or who are not post-menopausal defined as:

- Women who have had amenorrhea for \geq 12 consecutive months (without another medical cause) and who have a documented serum follicle-stimulating hormone (FSH) level $>$ 35 mIU/mL.
- Women who have irregular menstrual periods and a documented serum FSH level $>$ 35 mIU/mL.
- Females of childbearing potential must have a negative pregnancy test within 7 days prior to the initiation of treatment.

Pregnancy tests will be performed in WOBCP at the following visits: Visit 1 (week 0), 4 (week 4), 6 (week 14), 7 (week 26), 8 (Week 39), and 9 (week 52). Should this test be positive, then the patient will be immediately withdrawn from the trial and study drug will be discontinued.

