Should a patient develop symptomatic heart failure during the study they will be offered open-label sacubitril/valsartan. Patients starting open-label sacubitril/valsartan or withdrawing from study medication (or study follow-up) ≥ 6 months after randomisation will be asked to undergo an end-of-study CMR examination (patient withdrawing before 6 months will not be asked to have a second CMR as an effect of LV remodelling is unlikely to be detected before this time point).

The emergence of the following circumstances will require permanent study drug discontinuation:

- Withdrawal of informed consent
- Investigator thinks that continuation of study drug would be detrimental to the patient's well-being
- Suspected or confirmed occurrence of clinically significant angioedema. A patient with any signs or symptoms of clinically significant angioedema should be thoroughly evaluated by the investigator
- Pregnancy and post-pregnancy during lactation period

The emergence of the following circumstances will require temporary or permanent discontinuation (study drug may be restarted once these circumstances no longer exist):

- Use of an open label ACE inhibitor, ARB, direct renin inhibitor, lithium, cholestyramine or colestipol resins (*Table 6-1*)
- Any laboratory abnormalities that in the judgment of the investigator warrant discontinuation of study drug after taking into consideration the patient's overall condition

Study drug may be discontinued at the investigator's discretion if any of the following occurs:

- Any severe suspected drug-related AE

- Any other protocol deviation that results in a significant risk to the patient's safety
- Subsequent clinical need for implantable cardiac device insertion (e.g. permanent pacemaker, implantable cardioverter defibrillator, cardiac resynchronisation therapy)

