Any ARB	Discontinue study drug. The open label ARB must be stopped prior to re-initiation of study drug
Any direct renin inhibitor	Discontinue study drug. The open label direct renin inhibitor must be stopped prior to re-initiation of study drug
Entresto (commercially available sacubitril/valsartan)	Discontinue study drug. The open label Entresto must be stopped for ≥ 36 hours prior to re-initiation of study drug
Lithium	Discontinue study drug. Lithium must be stopped prior to re-initiation of study drug
Cholestyramine or colestipol resins	Discontinue study drug. Cholestyramine or colestipol resins must be stopped prior to re-initiation of study drug

The concomitant use of open-label ACE inhibitor, ARBs, commercially available sacubitril/valsartan (Entresto) or a direct renin inhibitor is **strictly prohibited** while the patient is receiving study drug. If the addition of an ACE inhibitor, ARB, Entresto or direct renin inhibitor is necessary, then study drug must be temporarily discontinued. If the patient is to be started on open-label ACE inhibitor or Entresto, the study drug must be stopped ≥ 36 hours prior to initiating ACE inhibitor or Entresto. If study drug is to be re-started, the open-label ACE inhibitor or Entresto must also be stopped ≥ 36 hours prior to re-initiating study drug. ARBs or a direct renin inhibitor should be stopped prior to resuming study drug.

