8.2.2 CMR protocol

All CMR scans will be performed on a single 3.0 Tesla Siemens MAGNETOM Prisma scanner located in the CRF at the QEUH. The MRI scan will include cine MRI, T1 and T2 maps, strain encoded MRI, and contrast enhanced imaging including first pass perfusion at rest, microvascular obstruction and late gadolinium enhancement imaging 10 - 15 min after contrast administration. IV access will be required for contrast administration and a full blood count will be obtained before the scan in order to measure extracellular volume. Specific details of the CMR protocol are detailed in a local Standard Operating Procedure. Patients will be provided with an MRI information sheet prior to their visit (Appendix 2).

8.3 26-week visit

This will comprise of a half-day visit to the QEUH CRF. A number of the baseline investigations will be repeated:

- full physical examination
- spot urine collection
- venepuncture – 50ml blood withdrawn for biochemical and hormonal analysis

Patients will also be asked to complete a short patient global assessment questionnaire (Appendix 3) at this visit.

8.4 52-week visit (+/- 3 months)

This will comprise of a half-day visit to the QEUH CRF. A number of the baseline investigations will be repeated:

- full physical examination
- spot urine collection
- venepuncture – 50ml blood withdrawn for biochemical and hormonal analysis
- cardiac MRI with gadolinium contrast will be performed.

Patients will also be asked to complete a short patient global assessment (Appendix 3) questionnaire at this visit.

In response to the COVID-19 pandemic we have allowed an extension of the patients IMP treatment by up to 3 months. During this extended time on IMP we would anticipate following up with patients by telephone every 6 weeks. Patients have the clinical research team contact details should they wish to discuss any aspect of the extended involvement themselves.

At this point a patient's participation in the involvement in the trial will end. They will return any unused study drug. Following their involvement in the trial patients will be converted to an ACE-inhibitor or ARB as per local practice guidelines at an equivalent dose to their final study drug dose level. Prior to commencement of any ACE-inhibitor, patients will require to have a 36-hour washout period following their last dose of study drug in order to reduce the risk of angioedema associated with combined ACE and NEP inhibition.

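### Section 6.9 converts any withdrawing patient to an ACE inhibitor or ARB whatever the reason, unreconciled with the angioedema and pregnancy withdrawals and without pointing to the 36-hour washout

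*Protocol*

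**What the plan says.** Protocol Section 6.9 (Withdrawal of treatment) opens with the patient's right to leave: any enrolled patient is "free to withdraw from the study at any time without giving reason". It then says that "any patient withdrawing will be converted to an ACE-inhibitor or ARB as per local practice guidelines at an equivalent dose" to the last study drug level. It names no exception by reason for withdrawal, no washout and no other section. Section 4.1 carries a near-identical conversion sentence for patients who complete treatment, also without a washout.

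Other sections bear on the same patients:

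- Section 6.8.4, directly before 6.9, says of study drug after angioedema: "It must not be re-administered. Any patients who experience angioedema during the trial will be withdrawn from the study".
- Section 5.3 says of a pregnancy test in women of childbearing potential: "Should this test be positive, then the patient will be immediately withdrawn from the trial and study drug will be discontinued". Section 6.5 lists both clinically significant angioedema and pregnancy as grounds for permanent discontinuation.
- Section 6.6 says: "If the patient is to be started on open-label ACE inhibitor or Entresto, the study drug must be stopped" at least 36 hours beforehand.
- Section 8.4, for the end of participation, says: "Prior to commencement of any ACE-inhibitor, patients will require to have a 36-hour washout period following their last dose of study drug".

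**The concern.** Section 6.9 is the only section headed for withdrawal, and its wording is directive: the patient will be converted, and at an equivalent dose. Some patients leave because the protocol takes them off a drug for safety. If 6.9 is applied to them literally, the protocol withdraws them from an ARB-containing drug in one section and directs them to an ACE inhibitor or ARB in the next. The two groups for whom this matters are those withdrawn for angioedema and those withdrawn for pregnancy.

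A second, smaller gap concerns the washout. The protocol uses a 36-hour interval to limit angioedema risk from overlapping ACE and neprilysin inhibition. Someone reading only 6.9 or 4.1 at the moment of a switch would not see it.

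What is at stake is patient safety and consistent handling of withdrawals, not the estimate of the treatment effect.

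**Working it through.** No figure in the plan is at issue, so there is nothing to recompute. The check sets the passages side by side.

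**Step 1: whom does 6.9 cover?** Two readings are possible. The narrow reading takes its cue from the opening sentence and covers voluntary withdrawal only. The broad reading takes the section title and the word any at face value and includes patients withdrawn by protocol rule.

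**Step 2: compare each reason for withdrawal with 6.9.**

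| Reason | What the protocol says elsewhere | What 6.9 adds on the broad reading | Relation |
|---|---|---|---|
| Angioedema | 6.8.4: withdrawn, study drug never given again. 6.5: permanent discontinuation. 5.2: a history of angioedema bars entry. 6.4: each arm is sacubitril/valsartan or valsartan, so each contains an ARB | Conversion to an ACE inhibitor or ARB at equivalent dose | Conflict, by inference |
| Pregnancy | 5.3: immediate withdrawal. 6.5: permanent discontinuation. 7: developmental toxicity cannot be ruled out. 5.4: ACE inhibitors and ARBs are described as similar to the study medicines | Conversion to an ACE inhibitor or ARB at equivalent dose | Conflict, by inference |
| Any switch to an ACE inhibitor | 6.6 and 8.4: 36 hours off study drug first | Silent | Missing cross-reference |

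The angioedema and pregnancy rows rest on inference because the rules in 5.3, 6.5 and 6.8.4 govern study drug, and 5.2 governs entry. None of them says that an ACE inhibitor or ARB may not be given afterwards. The similarity remark in 5.4 is made in the section on male participants, so it supports the pregnancy inference only indirectly.

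**Step 3: does the narrow reading remove the problem?** Not fully. If 6.9 covers voluntary withdrawal only, no section deals specifically with follow-on ACE inhibitor or ARB treatment for patients withdrawn for angioedema or pregnancy. The general sentence in 4.1 about the end of involvement makes no exception either. The text needs clarifying on both readings.

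**Step 4: the washout.** The 6.6 rule applies whenever an open-label ACE inhibitor is to be started after study drug, and it refers to study drug without distinguishing the arms. It therefore reaches a withdrawing patient. Section 8.4 states the interval for the end of participation, which is the situation that the 4.1 sentence describes. Neither 6.9 nor 4.1 permits a shorter gap. They simply do not mention it.

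**The case against.** The strongest defence is that 6.9 opens with voluntary withdrawal, that protocol-driven stops have their own rules in 5.3, 6.5 and 6.8.4, and that the reference to local practice guidelines leaves room for clinical judgement. On that view no site would convert a pregnant patient or one with angioedema on the strength of 6.9. Part of this stands: the conflict depends on the reading, and it is an assumption that a site would apply 6.9 literally. It does not remove the need for a change, because the sentence itself is unqualified and directive.

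A reader might also infer stronger points that the documents do not support:

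- *That 6.9 lets an ACE inhibitor start without the 36-hour gap.* Sections 6.6 and 8.4 already require the gap, and silence in 6.9 does not override them.
- *That 6.9 collides with the heart-failure rule.* Section 6.5 says "Should a patient develop symptomatic heart failure during the study they will be offered open-label sacubitril/valsartan". It then lists patients who start open-label drug separately from those who withdraw, so they need not fall under 6.9 at all.
- *That an equivalent dose can be found only for dose level 2.* The title of Table 4-1 is indeed limited in that way ("Total daily doses of commonly used ACE inhibitors or ARBs corresponding to ramipril 2.5mg BD (dose level 2 of study drug"), and Section 4.1 uses the table for entry and starting dose. But Table 4-2 pairs a valsartan dose with each of the three levels, and Section 4.2 equates valsartan exposure at level 3 with valsartan 160 mg BD. Only other agents at levels 1 and 3 are untabulated, and 6.9 refers conversion to local guidelines.
- *That about 10 of the 100 patients would be affected.* The 10% in Section 11.1 is made up of loss to follow-up, development of heart failure and death. None of these is plainly a 6.9 withdrawal.

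**Conclusion.** The point holds in a limited form. The conversion sentence in 6.9 is not qualified by the reason for withdrawal and, read as written, conflicts by inference with the angioedema and pregnancy withdrawals. Sections 6.9 and 4.1 also lack a cross-reference to an existing washout rule.

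Its size cannot be stated as a number. The documents give no expected count of withdrawals, angioedema cases or pregnancies, and none can be derived from the sample-size section. No effect on the primary endpoint or its analysis is shown. The collection of serious adverse events for 30 days after treatment stops (Section 10.2) is ordinary safety capture and not a harm caused by 6.9.

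The conclusion assumes that 6.9 may be read to include patients withdrawn by protocol rule. If it may not, what remains is that their follow-on treatment is not specifically addressed. Because patient safety is involved and the change is small, the text should be corrected.

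**What to change.** Reconcile Section 6.9 with Sections 5.3, 6.5 and 6.8.4 by making the conversion sentence subject to the reason for withdrawal, and state whether 6.9 covers voluntary withdrawal only or also withdrawal under a protocol rule. In both 6.9 and 4.1, add a cross-reference to the 36-hour requirement already stated in 6.6 and 8.4. What treatment, if any, should follow each type of withdrawal is a clinical matter for the investigators and the sponsor to settle.

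The cost is revised wording in two protocol paragraphs, made through an amendment with a note to site staff. It needs no extra visits or data and no change to the SAP.

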6.10 Unblinding procedure

Breaking of the study blind in an emergency should only be performed where knowledge of the treatment is absolutely necessary for further management of the patient. In case of any acute illness or major surgery, the study medication should be discontinued. Emergency unblinding will be available at all times, via the telephone (Interactive Voice Response System, IVRS). Details are included in the study alert card. For each unblinding request an email alert will be sent to the appropriate members of the research team, including the Chief Investigator (CI).

Patients will be provided with an alert card at the randomisation visit after verbal consent is obtained. They will be asked to carry the alert card with them at all times and to show the card to any doctors or healthcare professionals who are involved in their care. Patients will also be asked at study visit 4 if they still have this and be provided with another if required. The Patient Alert Card will be collected from patients at the end of their involvement in the study.

Unblinding the treatment allocation may be required when reporting suspected unexpected serious adverse reactions (SUSARs) to the regulatory authorities. This will be performed by the Sponsor PV Office.

7 Assessment and management of risk

The risk to patients participating in the study will be minimised by compliance with the inclusion/exclusion criteria and close clinical monitoring.

Patients will be instructed not to take any RAAS blockade medications (ACE inhibitor or ARB) from the day they start study drug to avoid excess RAAS blockade. The importance of a minimum 36-hour washout period prior to commencement of study drug in patients receiving ACE-inhibitors prior to randomisation will be reiterated to minimise the risk of angioedema. The risk of discontinuation of pre-randomisation ACE inhibitors or ARBs will be minimal as the study treatment will be reflective of the typical dosing schedule of most ACE inhibitors and ARBs. All patients will be required to continue receiving the rest of their standard of care background cardiovascular medications.

In women of child-bearing potential, a possible risk of developmental toxicity cannot be excluded. Women of child-bearing potential should therefore use a highly effective method of contraception during study participation. If there is any question that the patient will not reliably comply, they should not be entered in the study. Pregnancy testing will be performed prior to randomisation and at regular intervals during the study in women of child-bearing potential.

8 Visit schedule and assessments

Table 9-1 details all of the visits and indicates with an “x” when study assessments or procedures are performed. Patients should be seen for all visits at the designated time or as close to as possible. These visits windows are what investigators should endeavor to stick to and wherever possible should be met. Any visits out with these timeframes will not be considered protocol violations but will be dealt with in the statistical analysis plan.

8.1 Screening

Potentially eligible patients will be identified through the “post-MI LVSD” clinic or general cardiology out-patient clinics in NHS Greater Glasgow and Clyde (NHS GG&C) and surrounding health boards. Additionally, participants will be identified from electronic searching of the cardiac patient database by a clinical research fellow, who is a member of the direct clinical care team. They will also be identified by clinicians and nurses responsible for the routine care of these patients, for example cardiac rehabilitation nurses, cardiology pharmacists and cardiologists.

Potential participants will be approached in one of two ways:

(1) Approach in person by the clinical care team at a routine outpatient appointment. Those who demonstrate interest will be given the patient information sheet (PIS),

and asked for verbal consent for their details to be passed to the research team. The PIS will contain a contact email address and telephone number to allow patients to “opt in” to the study or get in contact for further information. If there has been no contact from a patient 48 hours after being given the PIS the patient will be telephoned by a clinical fellow or research nurse to ascertain interest in participation in the study.

(2) Letter drop: letters posted to the patient by the principal investigator with information about the study. The same contact information will be provided for patients contacted by letter drop to allow them to opt in to the study. These patients will also be contacted 5-7 days after posting the letter by a clinical fellow to assess interest in participating in the study; Initial screening will be based on a telephone discussion with the potential patient who has expressed an interest in participating in the study supported by a review of their health records by a clinical fellow, as part of their routine clinical care team, and the research team. Where possible, any missing biochemical data required as an inclusion criterion will be ordered ahead of enrolment as part of standard of care if unrecorded in the last 6 months. This is to ensure appointments for screening echocardiography are only made for patients considered suitable to enter the study and avoid unnecessary inconvenience if they are not thought to be eligible based on routine information. Telephone discussions with the patient would also aim to ensure their ability to adhere with the trial, diagnostic tests, outcomes measures, and their ability to give informed consent. If the potential participant wishes to discuss any aspect of the study, they will be given the opportunity to do so with a member of the research team either over the phone or at the screening study visit and before consent is taken.

If agreeable and eligible on review of their medical case notes, assenting patients will then proceed to screening echocardiography. Patients will be consented for screening echocardiography and routine biochemical blood tests (U&Es and LFTs) if unrecorded in the last 6 months to ensure trial eligibility.

